#### Analysis sets:

The Intent to Treat (ITT) population includes all subjects randomly allocated to a treatment. The Modified Intent to Treat (MITT) population includes all subjects in the ITT Analysis Set who receive at least one dose of study drug, have a baseline, and at least one post baseline efficacy assessments. The Per-Protocol (PP) population includes all subjects in the MITT Analysis Set who have no important protocol deviations affecting the assessment of efficacy. Membership of the PP Analysis Set will be confirmed prior to unblinding the data. The ITT, MITT and PP populations will be analyzed per planned treatment.

The Safety population is all subjects who receive at least one dose of study treatment. The Safety population will be analyzed per the actual treatment received.

#### Primary analysis:

The primary endpoint is achievement of an IGA score of 0 or 1 at 12 weeks. The response rate for the IGA score of 0 or 1 at Week 12 is defined as the proportion of subjects at Week 12 with an IGA score of 0 or 1 and with a reduction from baseline IGA of 2 points or more. Baseline IGA score is the last score prior to the first dose of study medication. Any missing IGA score of 0 or 1 response will be imputed as a non-response.

The primary analysis will be based on the ITT Analysis Set. The primary treatment comparisons will be made using the two-sided Cochran-Mantel-Haenszel (CMH) test stratified by prior biologic use (yes/no) and body weight stratum ( $\leq 90\text{kg}$ ,  $>90\text{kg}$ .)

#### Sensitivity analyses:

The primary analysis will be repeated on the MITT and PP Analysis Sets. Furthermore, selected sensitivity analyses will be performed on the ITT Analysis Set, including multiple imputation and last-observation carried forward.

#### Secondary analyses:

Secondary efficacy and QoL endpoints will be compared between treatments at each visit up to Week 48 using the CMH test for binary endpoints and an Analysis of Covariance (ANCOVA) model for changes from baseline.

Safety data will be summarized in the Safety Analysis Set by treatment and over time, for each treatment period separately and overall.

Exploratory analyses:

Exploratory analyses of efficacy will be made for (i) all subjects who were dose-escalated at Week 12, and (ii) all subjects who had active treatment withheld following an IGA score of 0 at Week 24.

Subgroup analyses:

Subgroup analyses of key efficacy and safety data will be performed as appropriate by geographical region, prior biological use, weight category, gender and geriatric status.

Interim analyses:

[figure not shown]
An independent Data Monitoring Committee (DMC) will be established to perform and review interim analyses during the study. The DMC will be operational prior to enrolment of the first subject into the study. The composition and operation of the DMC will be described in a DMC charter. The charter will also detail how the communication between the DMC and the sponsor will be firewalled to preserve the blinding and integrity of the study.

The DMC will closely monitor the safety and tolerability data throughout the trial. No formal analysis of efficacy is planned during the double-blind, placebo-controlled 12-week induction phase.

An unblinded interim analysis of 12-week data will occur at the completion of the Week 12 period, while the study is still ongoing. These data will be shared with firewalled individuals who are not directly involved in the conduct of the study.

A second interim analysis will occur at the completion of the Week 24 period. All investigators and subjects will remain blinded to treatment assignments until the last subject completes the study and the final database lock occurs. Once the second interim database lock has occurred after Week 24, the sponsor study team will be unblinded.

1.2 Schema

\* Prior to Week 24

M1095 subjects in Arms 2 and 3 will receive placebo at Week 1, 3, 6, 10 and 14.

M1095 subjects in Arm 4 will receive placebo at Week 1, 3, 6, 10, 14 and 16.

M1095 subjects in Arm 5 will receive placebo at Week 1, 3 and 14.

Secukinumab subjects in Arm 6 will receive placebo at Week 6, 10 and 14.

1.3 Schedule of Activities (SoA)

Visit	Screening	1	2	3	4	5	6	7	8	9	10	11	12	13	14	15	16	17	18	19	20	Early D/CA
Week	N/A	0	1	2	3	4	6	8	10	12	14	16	20	24	28	32	36	40	44	48	52	N/A
Day	-28 to -1	1	8	15	22	29	43	57	71	85	99	113	141	169	197	225	253	281	309	337	365	N/A
Visit Window (in days)	N/A	N/A	±1	±1	±1	±1	±2	±2	±2	±2	±2	±2	±2	±2	±5	±5	±5	±5	±5	±5	±5	N/A
Informed Consent	X																					
Demographics	X																					
Inc/Exc Criteria	X	X																				
Psoriasis Medical History	X																					
Prior Psoriasis Treatments	X																					
Other Medical History	X																					
Adverse Events	X B	X	X	X	X	X	X	X	X	X	X	X	X	X	X	X	X	X	X	X	X	X A
Concomitant Medications	X	X	X	X	X	X	X	X	X	X	X	X	X	X	X	X	X	X	X	X	X	X A
Skin Evaluation C	X C	X C	X C	X C	X C	X C	X C	X C	X C	X C	X C	X C	X C	X C	X C	X C	X C	X C	X C	X C	X C	X A,C
Physical Examination	X D	X				X	X	X	X	X	X	X	X	X	X	X	X	X	X	X	X	X A
Vital Signs	X	X	X	X	X	X	X	X	X	X	X	X	X	X	X	X	X	X	X	X	X	X A
Laboratory Analysis Chemistry and Haematology (central)	X			X		X		X			X	X	X		X	X		X	X		X	X A
Laboratory Analysis Chemistry and Haematology (central, fasting)		X								X				X		X				X		
Urinalysis (local)	X	X								X				X		X				X		X A
Serum Pregnancy Test (central)	X																					
Urine Pregnancy Test (local)						X E		X E		X E		X E	X E	X E	X E	X E	X E	X E	X E	X E	X E	X A,E
QuantiFERON®-TB Gold Test	X F																					
HBV, HCV, HIV Test (central)	X																					

Visit	Screening	1	2	3	4	5	6	7	8	9	10	11	12	13	14	15	16	17	18	19	20	Early D/C A	
Week	N/A	0	1	2	3	4	6	8	10	12	14	16	20	24	28	32	36	40	44	48	52	N/A	
Day	-28 to -1	1	8	15	22	29	43	57	71	85	99	113	141	169	197	225	253	281	309	337	365	N/A	
Visit Window (in days)	N/A	N/A	±1	±1	±1	±1	±2	±2	±2	±2	±2	±2	±2	±2	±2	±5	±5	±5	±5	±5	±5	±5	N/A
ECG standard 12 lead (central)	X									X							X			X		X A	
Blood sample for Immunogenicity (pre-dose)		X		X		X		X		X				X			X		X	X	X G	X AG	
Blood sample for Pharmacokinetics (pre-dose)		X		X		X		X		X				X			X		X	X	X	X A	
BSA	X	X	X	X	X	X	X	X	X	X	X	X	X	X L	X	X	X	X	X	X	X	X	X A
PASI	X	X	X	X	X	X	X	X	X	X	X	X	X	X L	X	X	X	X	X	X	X	X	X A
IGA	X	X	X	X	X	X	X	X	X	X	X	X	X	X L	X	X	X	X	X	X	X	X	X A
DLQI H		X								X				X			X			X		X A	
EQ-PSO H		X								X				X			X			X		X A	
SF-36 H		X								X				X			X			X		X A	
PHQ-8 H		X				X				X		X	X	X	X	X	X	X	X	X	X	X A	
eC-SSRS H		X				X		X		X		X	X	X	X	X	X	X	X	X	X	X A	
Chest X-Ray	X I																						
Randomization (via IRT)		X																					
Study Treatment (allocated via IRT)		X	X	X	X	X	X	X	X	X J	X	X	X	X K	X	X	X	X	X				

- A. See Section 8.1.11 - Early Discontinuation Visit should be performed as close as possible to 28 days after the last dose of study drug, and prior to the initiation of any other biological therapy. The reason for discontinuation should be discussed with the Medical Monitor. All subjects should have further follow up by telephone, or if they have ongoing SAEs or AEs, by attending the study site approximately 8 weeks (56 days) after the last dose of study drug to report any new, and follow up any existing AEs. Subjects that have completed Early Discontinuation from study treatment will continue to be contacted by telephone as per the q4w study schedule up to Week 52.
- B. AEs to be collected from the time of consent.
- C. On skin evaluation, if a subject develops a cutaneous rash that is not typical of a psoriatic picture, the following evaluations should be conducted – photograph, skin biopsy, and skin culture for microbiological assessment. Any such rash should be discussed with the Medical Monitor (see Section 8.4.2 for details).
- D. Physical examination includes subject's weight. Subject's height is measured only within the physical examination at Screening.

- E. If a urine pregnancy test is positive, study treatment must be withheld. A serum pregnancy test (central) should be performed. See Section 10.4, Appendix 4 for details.
- F. Quantiferon TB test must be study specific and can be performed either by the central or local laboratory. If a Quantiferon TB test result is 'indeterminate' the test must be repeated during the Screening period. If any Quantiferon TB test is 'positive' or if the first test and the repeat test are both 'indeterminate', the subject must be referred for tuberculosis workup per local guidelines. The subject is eligible for randomization if (i) they have a known history of latent TB and have completed a course of treatment or (ii) they have received sufficient treatment for latent TB to allow concomitant treatment with a biological therapy as per local guidelines (note these subjects must continue their concomitant latent TB treatment to completion while participating in the study, and if these subjects are outside of the screening window (>28 days since consent) when they become eligible to participate, they should be fully re-screened for the study). The subject is not eligible for randomization if either 'active tuberculosis is present' or if 'latent tuberculosis is present and is untreated per local guidelines.'
- G. Subjects that test positive for anti-drug antibodies at the last study visit (either Week 52 or Early Discontinuation) may be requested to provide another sample approximately 6 to 12 months after study completion.
- H. Patient Reported Outcomes should be conducted at the start of each visit, before other assessments.
- I. Chest X-ray within 3 months of consent is considered acceptable. When performed as part of the Screening visit, the chest X-ray should be the last study procedure to be completed, as this will prevent unnecessary exposure to radiation if the subject is found to be ineligible following an earlier procedure. Investigator should follow up the results of the chest X-ray with the Medical Monitor if clinically indicated.
- J. Subjects randomized to M1095 30mg or 60mg who do not achieve an IGA score of 0 or 1 at Week 12 will be dose escalated to 120mg q4w. All study drug is allocated via IRT.
- K. Any subjects randomized to M1095 who did not undergo dose escalation at Week 12 and who achieve an IGA score of 0 at Week 24 will have study drug withheld and will receive placebo q4w. Subsequently, if IGA score is 1 or more, these subjects will re-commence M1095 at the dose they received prior to Week 24 on a q4w regimen at the visits scheduled by the protocol until the end of the treatment period. Dose will not be withheld for a second time, irrespective of subsequent IGA scores. All study drug is allocated via the IRT.
- L. The investigator should carefully consider the subject's response at Week 24 and if there has been a worsening of psoriasis compared to baseline then the investigator should consider discontinuing the subject from the study if they are not receiving adequate benefit from their participation.

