## 6.6 Dose Modification

### 6.6.1 Week 12

Subjects randomized to placebo will receive M1095 120mg at Week 12, 14, 16 and then q4w.

Subjects randomized to M1095 30mg or 60mg and who do not achieve an IGA score of 0 or 1 at Week 12 will be dose escalated to receive M1095 120mg q4w.

Site personnel will enter the IGA score into the IRT prior to the study drug kit being assigned at Week 12.

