There is a visit window of  $\pm 1$  day for the Week 4 visit.

Patient reported outcomes (PRO) i.e. PHQ-8, and eC-SSRS should be performed before any other study procedures, assessments or consultations.

IGA, BSA and PASI should be conducted after the PROs and before other tests, procedures and consultations.

Study drug should be administered after completion of all other study procedures.

The following assessments will be performed and information collected:

- PHQ-8
- eC-SSRS
- IGA
- BSA
- PASI
- AEs
- Concomitant Medications
- Skin Evaluation
- Physical Examination
- Vital Signs
- Laboratory Analysis Chemistry and Haematology (Central Laboratory)
- Urine Pregnancy Test (Local) – if positive, study drug must be withheld and a Serum Pregnancy Test (Central Laboratory) performed

- Blood Sample for Immunogenicity (must be pre-dose)
- Blood Sample for Pharmacokinetics (must be pre-dose)
- Study Treatment (allocated via IRT)

#### 8.1.6 Weeks 8, 44, 52

There is a visit window of  $\pm 2$  days for Week 8, and  $\pm 5$  days for Weeks 44 and 52.

Patient reported outcomes (PRO) i.e. PHQ-8, and eC-SSRS should be performed before any other study procedures, assessments or consultations.

IGA, BSA and PASI should be conducted after the PROs and before other tests, procedures and consultations.

Study drug should be administered **after** completion of all other study procedures.

The following assessments will be performed and information collected:

- PHQ-8
- eC-SSRS
- IGA
- BSA
- PASI
- AEs - SAEs and AEs will be followed until resolution, stabilization or the event is otherwise explained or the subject is lost to follow up (see Section 7.3). AEs not considered serious or as an AESI will be considered ongoing if they have not resolved by Week 52.
- Concomitant Medications
- Skin Evaluation
- Vital Signs
- Laboratory Analysis Chemistry and Haematology (Central Laboratory)
- Urine Pregnancy Test (Local) – if positive, study drug must be withheld and a Serum Pregnancy Test (Central Laboratory) performed
- Blood Sample for Immunogenicity (must be pre-dose) – subjects testing positive at Week 52 may be requested to provide another sample 6 to 12 months after study completion
- Blood Sample for Pharmacokinetics (must be pre-dose)
- Study Treatment (allocated via IRT) with the exception of Week 52

- At Week 52, male and female subjects of child bearing potential should be reminded that they must use highly effective contraception for a further 4 weeks

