### 8.1.7 Weeks 12, 24, 36, 48

There is a visit window of  $\pm 2$  days for Weeks 12 and 24, and  $\pm 5$  days for Weeks 36 and 48.

Fasting blood samples should be obtained, so the visit should be conducted in the morning and the subject should not have had breakfast.

Patient reported outcomes (PRO) i.e. DLQI, EQ-PSO, SF-36, PHQ-8, and eC-SSRS should be performed before any other study procedures, assessments or consultations.

IGA, BSA and PASI should be conducted after the PROs and before other tests, procedures and consultations.

Study drug should be administered **after** completion of all other study procedures.

The following assessments will be performed and information collected:-

- DLQI
- EQ-PSO
- SF-36
- PHQ-8
- eC-SSRS
- IGA
- BSA
- PASI
- AEs
- Concomitant Medications
- Skin Evaluation
- Physical Examination
- Vital Signs
- Laboratory Analysis Chemistry and Haematology (Fasting, Central Laboratory)
- Urinalysis (Local)
- Urine Pregnancy Test (Local) – if positive, study drug must be withheld and a Serum Pregnancy Test (Central Laboratory) performed
- ECG (Standard 12 Lead, Central ECG Laboratory)

- Blood Sample for Immunogenicity (must be pre-dose)
- Blood Sample for Pharmacokinetics (must be pre-dose)
- Study Treatment (allocated via IRT) with the exception of Week 48
- At Week 24, the investigator should carefully consider the subject's response and if there has been a worsening of psoriasis compared to baseline then the investigator should consider discontinuing the subject from the study if they are not receiving adequate benefit from their participation.

### 8.1.8 Week 14

There is a visit window of  $\pm 2$  days for the Week 14 visit.

IGA, BSA and PASI should be performed before any other study procedures, assessments or consultations.

Study drug should be administered **after** completion of all other study procedures.

The following assessments will be performed and information collected:-

- IGA
- BSA
- PASI
- AEs
- Concomitant Medications
- Skin Evaluation
- Vital Signs
- Laboratory Analysis Chemistry and Haematology (Central Laboratory)
- Study Treatment (allocated via IRT)

### 8.1.9 Week 16, 20, 28, 32, 40

There is a visit window of  $\pm 2$  days for Weeks 16 and 20, and  $\pm 5$  days for Weeks 28, 32 and 40.

Patient reported outcomes (PRO) i.e. PHQ-8, and eC-SSRS should be performed before any other study procedures, assessments or consultations.

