#### **8.4.4 Electrocardiograms**

12-lead ECG will be obtained as outlined in the SoA (see Section 1.3) using an ECG machine that automatically calculates the heart rate and measures PR, QRS, QT, and QTc intervals.

At each time point, triplicate ECGs are required. Three individual ECG tracings should be obtained as closely as possible in succession, but no more than 2 minutes apart. The full set of triplicates should be completed in less than 4 minutes.

ECG should also be performed at any time in the study if clinically indicated.

Digital ECGs will be transmitted to a central vendor who will assess ECG measurements for screening requirements prior to randomization.

The investigator is to assess ECG measurements for safety and should report any clinically significant findings as adverse events.

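### The SoA shows no Week 24 ECG where Section 8.1.7 lists one; if the SoA governs, Arm 1 subjects held at Week 24 and never restarted have no scheduled ECG on M1095

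*Protocol*

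**What the plan says.** **ECG schedule.** The SoA row "ECG standard 12 lead (central" carries marks at Screening, Weeks 12, 36 and 48 and Early Discontinuation. The Week 24 cell is empty. The section headed "8.1.7 Weeks 12, 24, 36, 48" gives one procedure list for all four visits and includes "ECG (Standard 12 Lead, Central ECG Laboratory" with no exception for Week 24. That list does state an exception where one is meant: study treatment is not given at Week 48. Section 8.4.4 says "12-lead ECG will be obtained as outlined in the SoA (see Section 1.3", which sends the reader back to the table with the blank. It adds that an "ECG should also be performed at any time in the study if clinically indicated".

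**PHQ-8 schedule.** For Weeks 8, 44 and 52, Section 8.1.6 says "Patient reported outcomes (PRO) i.e. PHQ-8, and eC-SSRS should be performed before any other study procedures". The SoA row for PHQ-8 is blank at Week 8, while the eC-SSRS row directly below it is marked there.

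**Dosing in Arm 1.** Section 6.6.1: "Subjects randomized to placebo will receive M1095 120mg at Week 12, 14, 16 and then q4w". Section 8.1.7 also says "Study drug should be administered after completion of all other study procedures", so the Week 12 ECG in Arm 1 precedes any M1095. An Arm 1 subject with IGA 0 at Week 24 is switched to placebo and restarts only if a later IGA is 1 or more (Section 6.6.2). SAP Table 4.10 gives the M1095 doses of a held Arm 1 subject as Weeks 12, 14, 16 and 20.

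**ECG analysis.** SAP 4.9.2.3 reports ECG change from baseline and QT/QTc outliers for the induction period and the overall study, with no on-treatment limit. SAP 4.9.2.4 does limit its worst-value laboratory shift tables to on-treatment values. Arm 1 counts in the Total M1095 column for the overall period (SAP Table 4.3), with its baseline taken before the first M1095 dose, planned at Week 12 (SAP 4.1).

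**The concern.** Two parts of the protocol give different ECG schedules, and the section that should settle the matter points to only one of them. A site can follow either text and deviate from the other, so Week 24 ECG coverage, and Week 8 PHQ-8 coverage, could vary by site.

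ECGs are a named secondary safety assessment. For Arm 1 and for escalated subjects, a Week 24 ECG would be the only scheduled ECG in their first 12 weeks on 120 mg. For held subjects it would be the last one before drug is withheld. If it is not taken, some Arm 1 subjects enter the overall M1095 ECG and QTc tables only with tracings recorded long after the drug has gone. In a descriptive safety table that dilutes any effect of M1095. At the second interim analysis, an Arm 1 subject who has not reached Week 36 by the cut-off would add no scheduled ECG after M1095.

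**Working it through.** **1. Is the ECG row simply shifted?** Matching cells to the Week header, the ECG marks fall at Screening, 12, 36, 48 and Early Discontinuation. Two rows from the same half of the table serve as controls:
- DLQI: 0, 12, 24, 36, 48 and Early Discontinuation.
- Immunogenicity: 0, 2, 4, 8, 12, 24, 36, 44, 48, 52 and Early Discontinuation.

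All three rows have the same number of cells, and both controls agree with the ECG row at Weeks 12, 36 and 48. A shift does not explain the blank. This check cannot exclude a single lost mark.

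**2. The documents' own window.** Protocol 8.5.4 equates 8 weeks with 5 terminal half-lives, and Section 2.3 gives a half-life of 11 to 12 days. 56/11 = 5.1 and 56/12 = 4.7, so the figure reproduces. SAP 4.7.1 also treats a subject as exposed for 56 days after the last M1095 dose before a hold. I therefore call an ECG on drug if it falls within 56 days of the most recent M1095 dose.

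**3. Days from the most recent M1095 dose to each ECG scheduled in the SoA**, at nominal visit times, ECG before dosing:

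| Subject | Week 12 | Week 36 | Week 48 |
|---|---|---|---|
| Arm 1, held, never restarted | before first dose | (36−20)×7 = 112 | (48−20)×7 = 196 |
| Arm 1, held, restarted Week 28 or 32 | before first dose | (36−32)×7 = 28 | (48−44)×7 = 28 |
| Arm 1, held, restarted Week 36, 40 or 44 | before first dose | 112 | 28 |
| Arm 1, not held | before first dose | 28 | 28 |
| Arms 2 to 4 | (12−8)×7 = 28 | not needed | not needed |
| Arm 5 | (12−10)×7 = 14 | not needed | not needed |

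Only the first row has no entry of 56 days or less. Visit windows (±2 days at Week 20, ±5 at Week 36) move 112 to between 105 and 119, which changes nothing.

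**4. Drug remaining in the first row**, as 0.5^(days / half-life):
- Week 36: 112/11 = 10.2 and 112/12 = 9.3 half-lives, leaving 0.09% to 0.16% of the Week 20 dose.
- Week 48: 196 days, leaving less than 0.002%.

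**5. Gap between scheduled ECGs.** Under the SoA it is 36 − 12 = 24 weeks. Under Section 8.1.7 the longest gap from Week 12 is 12 weeks, and a held Arm 1 subject attending Week 24 has an ECG (24−20)×7 = 28 days after dosing, with 17% to 20% of the Week 20 dose remaining.

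**The case against.** The strongest objection is that the evidence is an empty cell in a table read from PDF, and the table shows damage. In the half that holds the ECG row, the Visit Window, BSA, PASI and IGA rows each have 23 entries for 22 columns. In the other half, fasting laboratory tests and urinalysis are marked at Week 32 where Section 8.1.7 has Week 36, and the Week 0 urine pregnancy test required by Section 8.1.2 is unmarked. This stands: the original page must be checked before the SoA is called wrong. The same caution applies to the Week 8 PHQ-8 blank. If the marks prove faithful, those other rows need the same comparison.

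It can also be said that safety reporting is descriptive, and that the optional dose-hold tables (SAP Table 4.15) already separate held from non-held subjects. That is fair, but they are produced only if deemed necessary. The committed overall-period ECG tables pool held with non-held subjects and on-drug with off-drug tracings.

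Three stronger readings are tempting and not supported:
- **That Weeks 12 to 24 have no ECG data.** Early Discontinuation and clinically indicated ECGs can still fall there. The SAP commits ECG tables only to induction and the overall study, so no committed table is emptied.
- **That held subjects generally lack an on-drug ECG.** Arms 2 to 5 have one at Week 12, and any Arm 1 subject who restarts has one at Week 48. Escalated subjects are not held, and their Week 36 and 48 ECGs are on drug.
- **That the planning PASI 100 range of 45 to 72% gives the number affected.** PASI 100 is not IGA 0. Section 4.3 ties the two ends to 30 mg and to the two-weekly 120 mg schedule, neither of which Arm 1 receives. Being held is also not the same as never restarting.

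**Conclusion.** As extracted, the SoA contradicts Section 8.1.7 on the Week 24 ECG and Section 8.1.6 on the Week 8 PHQ-8. If the SoA is followed, no scheduled ECG falls between Weeks 12 and 36, and Arm 1 subjects who are held at Week 24 and never restart have none within 56 days of an M1095 dose. They nevertheless contribute off-drug values to the overall M1095 ECG change and QTc outlier tables.

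The effect is confined to that subset of an arm of about 50. Its size depends on the IGA 0 rate at Week 24 and the rate of remaining at IGA 0, neither of which the documents give for Arm 1. The conclusion rests on the SoA marks being faithful to the original page, on nominal visit timing, and on the documents' 56-day window. It concerns safety data and leaves the primary endpoint untouched. It does not establish which of the two schedules was intended.

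**What to change.** 1. Check the original SoA page for lost marks in the ECG and PHQ-8 rows, and in the other rows that disagree with Section 8.1.
2. Reconcile the SoA with Sections 8.1.6 and 8.1.7 so that one ECG schedule and one PHQ-8 schedule apply at all sites. Which schedule is right is for the sponsor to decide. If a mark was only lost in extraction, nothing needs changing. Otherwise the cost is a text correction and notice to sites.
3. In SAP 4.9.2.3, restrict the overall-period M1095 ECG change and QTc outlier tables to ECGs within 56 days of the most recent active dose, and state how many subjects have no qualifying ECG. The length matches the SAP's 8-week window for treatment-emergent events. The anchor should be written as the last active dose, because held subjects continue to receive placebo as study drug. The downside is small: fewer ECGs per held subject in these tables. The planned listings still show every tracing.
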